## 6 Treatment

### 6.1 Study treatment

For this study, the term “investigational drug” refers to Novartis study drug ribociclib. Fulvestrant is also being used in this study. Study treatment in this study refers to the combination of drugs in each of the study arms and includes ribociclib/placebo and fulvestrant.

Ribociclib will be supplied by Novartis or its designee as 200 mg hard gelatin capsules as individual patient supply packaged in bottles.

Fulvestrant will be procured locally according to local practice and regulation, or supplied by Novartis (or its designee). Storage conditions are described in the medication label. Medication labels will comply with the legal requirements of each country and be printed in the local language.

All dosages prescribed and dispensed to the patient and all dose changes during the study must be recorded on the Dosage Administration Record eCRF.

The study met its primary efficacy endpoint (PFS) at the time of the primary analysis. It also met the secondary efficacy endpoint of OS at the time of the pre-planned 2nd interim OS analysis.

Given the demonstrated survival benefit, patients and investigators will be unblinded to the treatment allocation. Additionally, patients who remain on study and are currently allocated to the placebo + Fulvestrant arm, will be given the opportunity to transition to the ribociclib + Fulvestrant combination.

Unblinded study treatment period will end once a patient discontinues from the study treatment for any reason or the end of study (EOS) is declared, whichever occurs first.

Following protocol amendment 4 and the unblinding of study participants, the word “placebo” refers to the original treatment allocation in the study. Physical placebo capsules no longer need to be administered but the reference to placebo has been kept in places in the protocol to avoid confusion.

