### **6.3.2 Treatment assignment or randomization**

Patients will be randomized to one of the **two** treatment arms ([Section 4.1](#) and [Section 6.1](#)) in a ratio of 2:1.

Randomization will be stratified by the following factors:

1. Lung or liver metastases: (yes versus no)
2. Previous endocrine therapy

The randomization numbers will be generated using the following procedure to ensure that treatment assignment is unbiased and concealed from patients and investigator staff. A patient randomization list will be produced by the Interactive Response Technology (IRT) provider using a validated system that automates the random assignment of patient numbers to randomization numbers. These randomization numbers are linked to the different treatment arms, which in turn are linked to medication numbers. A separate medication randomization list will be produced by or under the responsibility of Novartis Global Clinical Supply (GCS) using a validated system that automates the random assignment of medication numbers to medication packs containing each of the study treatments.

Prior to dosing, all patients who fulfill all inclusion/exclusion criteria will be randomized via IRT to one of the treatment arms. The investigator or his/her delegate will call or log on to the IRT and confirm that the patient fulfills all the inclusion/exclusion criteria. The IRT will assign a randomization number to the patient, which will be used to link the patient to a treatment arm and will specify a unique medication number for the first package of study treatment to be dispensed to the patient. The randomization number will not be communicated to the caller.

Following protocol amendment 4, patients will be unblinded to their treatment allocation.

Additionally, patients who are currently allocated to the placebo combination arm and still on study treatment, will be given the opportunity to transition to the LEE011 combination.

Those patients on the placebo arm who do not wish to cross-over from placebo to LEE011 can remain on their current treatment allocation (i.e. fulvestrant alone).

All of the study treatment cross-over registration and dispensing will be managed by the study IRT system. After transition to the investigational treatment, placebo dispensing in IRT will stop. Comparator treatment (i.e. fulvestrant) will continue to be managed locally.

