2.1.8 On-treatment assessment/event

Safety summaries and selected summaries of deaths will summarize only on-treatment assessments/events.

Double-blind on-treatment period:

An on-treatment assessment/event is defined as any assessment/event in the following time interval:

[date of first administration of study treatment, the earliest between the date of last administration of study treatment + 30 days and the date of first administration of cross-over open-label ribociclib plus fulvestrant treatment – 1 day], i.e., including the lower and upper limits.

The double-blind on-treatment period is the **default** on-treatment period used in the analyses unless specified otherwise.

Cross-over on-treatment period:

An on-treatment assessment/event is defined as any assessment/event in the following time interval: [date of first administration of the cross-over open-label ribociclib plus fulvestrant treatment, date of last administration of the cross-over open-label ribociclib plus fulvestrant treatment + 30 days], i.e., including the lower and upper limits.

(Note: However, the calculation of study treatment duration will use different rules as specified in [Section 3.5.1](#)).

An AE started in the screening phase and ongoing in the on-treatment phase will not be considered as an on-treatment AE unless it has worsened.

If the last date of study treatment is missing, any assessment/event occurring after the start of study treatment will be considered as on-treatment.

Data listings will include all assessments/events, flagging those which are not on-treatment.

Note: The date of first administration of study treatment and the date of last administration of study treatment are defined in [Sections 2.1.4](#) and [2.1.5](#), respectively.

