3.7 Safety evaluation

The assessment of safety will be based mainly on the frequency of adverse events and on the number of laboratory/ECG values that fall outside of pre-determined ranges. Other safety data (e.g., vital signs and special tests) will be considered as appropriate.

All safety outputs will use the safety set. The safety summary tables will include ‘double-blinded on-treatment’ events/assessments, i.e., those collected on or after the first date of study treatment and collected no later than 30 days after the date of last study treatment administration or the date of the day prior to the start of cross-over open-label ribociclib plus fulvestrant treatment. The AEs started before the first dose but worsening during the treatment period are also considered as ‘on-treatment’ events.

Key safety analyses that include data from the cross-over on-treatment period will also be performed on the cross-over analysis set. See Section 2.1.8 for more details on the definition of ‘on-treatment’ event during the cross-over on-treatment period.

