3.7.1.4 AE summaries

The following adverse event summaries will be produced by treatment group:

- Summary of deaths and adverse events
- Adverse events, irrespective of causality, by primary system organ class, preferred term and maximum grade
- Adverse events with suspected relationship to study treatment by primary system organ class, preferred term and maximum grade
- Most common grade 3-4 adverse events, irrespective of causality, by preferred term and maximum grade (greater than x% in either arm)
- Adverse events, irrespective of causality, by primary system organ class and maximum grade
- Adverse events, irrespective of causality, by preferred term and maximum grade
- Adverse events with suspected relationship to study treatment by preferred term and maximum grade
- Grade 3 or 4 adverse events, irrespective of causality, by primary system organ class, preferred term and maximum grade
- Grade 3 or 4 adverse events with suspected relationship to study treatment by primary system organ class, preferred term and maximum grade
- On treatment deaths by preferred term
- Deaths, by primary system organ class and preferred term
- Serious adverse events, irrespective of causality, by primary system organ class and preferred term and maximum grade
- Serious adverse events with suspected relationship to study treatment, by primary system organ class, preferred term and maximum grade
- Adverse events leading to study drug discontinuation, irrespective of causality, by primary system organ class, preferred term and maximum grade
- Adverse events leading to study drug reductions, irrespective of causality, by primary system organ class, preferred term and maximum grade
- Adverse events leading to study drug interruptions, irrespective of causality, by primary system organ class, preferred term and maximum grade
- Adverse events requiring additional therapy, irrespective of causality, by primary system organ class, preferred term and maximum grade
- On-treatment deaths and SAEs with fatal outcome, by SOC and PT

AEs of interest will also be summarized. See [Section 3.7.1.5](#) for the grouping details.

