3.7.1.5 Grouping of adverse events of special interest

An adverse event of special interest is a grouping of adverse events that are of scientific and medical concern specific to ribociclib. These groupings are defined using MedDRA terms, SMQs (standardized MedDRA queries), HLGs (high level group terms), HLTs (high level terms) and PTs (preferred terms). Customized SMQs (Novartis MedDRA queries, NMQ) may also be used. A NMQ is a customized group of search terms which defines a medical concept for which there is no official SMQ available or the available SMQ does not completely fit the need. It may include a combination of single terms and/or an existing SMQ, narrow or broad. For each specified AESI, the number and percentage of patients with at least one event of the AESI occurring during the double-blinded on-treatment period will be summarized.

Summaries of these AESIs will be provided by treatment arm, (specifying grade, SAE, relationship, leading to treatment discontinuation, leading to dose adjustment/interruption, etc.).

A Case Retrieval Sheet (CRS) with the exact composition of the AE groupings is to be used to map reported AEs to the AESI groupings. This file may be updated (i.e., it is a living document) based on review of accumulating trial data, and therefore the groupings are also subject to potential change. The most up-to-date version of the CRS will be used at the time of the analysis.

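### The final SAP's 'double-blind' on-treatment period has no cut at the Amendment 4 unblinding, so open-label data, predominantly from the ribociclib arm, enter by-arm safety tables labelled double-blind

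*SAP*

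**What the plan says.** The SAP file holds two plans: one for the final study report, based on Amendment 4, and one for the primary PFS analysis, based on Amendment 2. This point concerns the first.

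- **Period definition (final SAP 2.1.8).** The double-blind on-treatment period starts at first study treatment. It ends at "the earliest between the date of last administration of study treatment + 30 days and the date of first administration of cross-over open-label ribociclib" (given with fulvestrant), the second date less one day. It is the default "on-treatment period used in the analyses unless specified otherwise".
- **Restated in the safety section (3.7).** Tables include data obtained "no later than 30 days after the date of last study treatment administration or the date of the day prior to the start of" treatment after cross-over. Sections 3.7.1.3 and 3.7.2 repeat the limit for adverse events and laboratory data. Sections 3.5.4 and 3.5.5 use the period for dose changes and discontinuations.
- **By-arm use.** Section 3.7.1.4: "The following adverse event summaries will be produced by treatment group". Section 3.7.1.5 reports the number and percentage of patients "with at least one event of the AESI occurring during the double-blinded on-treatment period will be summarized".
- **Unblinding (protocol 6.1).** "Given the demonstrated survival benefit, patients and investigators will be unblinded to the treatment allocation". The same section gives the time that follows its own name: "Unblinded study treatment period will end once a patient discontinues from the study treatment for any reason". Final SAP 1.1 also records that participants were unblinded with Amendment 4.
- **Placebo patients (protocol 6.3.2).** "Those patients on the placebo arm who do not wish to cross-over from placebo to LEE011 can remain on their current treatment allocation", meaning fulvestrant alone. Under final SAP 2.1.5 any component counts as study treatment, so fulvestrant alone keeps the period open.

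**The concern.** Until Amendment 4, protocol 4.1 and 10.7.2 kept investigators and patients blinded, even after a positive PFS result. Amendment 4 is therefore the point at which investigator-reported data change character. Whether an event is reported, whether it is judged related to treatment, and whether it leads to dose reduction, interruption or discontinuation can all depend on knowing the treatment. The final SAP tabulates each of these by arm under a label that tells the reader the data were blinded.

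The cut-off is also asymmetric. Ribociclib patients never cross over, so all their open-label time up to last dose + 30 days stays in. Placebo patients leave the period the day before their first cross-over dose and stay in only if they decline. Adjusting for exposure would not help, because the rates would still pool blinded and unblinded reporting.

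**Working it through.** **Reading check.** Who has post-unblinding data inside the period labelled double-blind?

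| Patient group at unblinding | Period ends at | Open-label data inside it? |
|---|---|---|
| Ribociclib arm, on treatment | last dose + 30 days | yes, all of it |
| Placebo arm, declines cross-over | last fulvestrant dose + 30 days | yes, all of it |
| Placebo arm, crosses over | day before first cross-over dose | only the gap since unblinding |

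The final SAP has no flag, split or sensitivity analysis at unblinding.

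**How one-sided is it?** The documents give no count of patients still on treatment, no cross-over uptake and no data cut-off. What follows is an estimate from planning inputs, with PFS standing in for time on treatment.

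*Inputs.* 727 patients were randomized (Amendment 3 rationale) at 2:1, so 727 × 2/3 = 484.7 and 727 × 1/3 = 242.3. Enrolment ran from June 2015 to June 2016 and Amendment 4 is dated 29 January 2020, which is about 43.5 to 55.5 months after randomization. Protocol 10.8 assumes control median PFS of 18 months (first line, 40%) and 6.5 months (second line, 60%), with hazard ratio 0.67.

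*The plan's own figures first.* Power = Φ(√(364 × 2/9) × |ln 0.67| − 1.96) = Φ(8.994 × 0.4005 − 1.96) = Φ(1.642) = 95%, as stated. 9/0.67 = 13.4 months, as stated. The 40/60 mixture gives a control median of 9.4 months against the stated figure of around 9.

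*Fraction progression-free at month t.*
- Placebo: 0.4 × 0.5^(t/18) + 0.6 × 0.5^(t/6.5)
- Ribociclib: 0.4 × 0.5^(t/26.9) + 0.6 × 0.5^(t/9.7), where 18/0.67 = 26.9 and 6.5/0.67 = 9.7

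At t = 43.5 these are 8.1% and 15.7%, or about 20 placebo and 76 ribociclib patients. At t = 55 they are 5.0% and 10.9%, or about 12 and 53. Averaged over uniform entry, they give 15.3 and 63.0 patients.

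*Ribociclib share of contributing patients at cross-over uptake u:* R/(R + P(1 − u)). For u = 0: 63.0/(63.0 + 15.3) = 80%. For u = 50%: 63.0/(63.0 + 7.65) = 89%.

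| Model | Ribociclib | Placebo | u = 0 | 50% | 90% | 100% |
|---|---|---|---|---|---|---|
| 40/60 mixture | 63.0 | 15.3 | 80% | 89% | 98% | 100% |
| Mixture with dropout hazard 0.0105, taken as monthly | 37.6 | 9.2 | 80% | 89% | 98% | 100% |
| Single exponentials, medians 13.4 and 9 | 38.1 | 5.6 | 87% | 93% | 99% | 100% |
| Mixture, no treatment effect (outside the planning assumptions) | 30.7 | 15.3 | 67% | 80% | 95% | 100% |

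Person-time shares over the next 24 months are similar (82% to 100% for the mixture). The formula counts decliners only. The short gap before a first cross-over dose is ignored, so 100% at full uptake is slightly too high.

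Amendment 4 needed ethics approval before implementation, so unblinding came after its date. Six months later the mixture gives 52.2 and 12.0 patients, and the share at zero uptake is 81%.

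**The case against.** The strongest reply is that the end rule follows the protocol. Section 10.5.3.1 defines on-treatment as first dose to 30 days after last dose, with no boundary at unblinding, and asks for a separate cross-over summary. That stands, and it is a good reason to keep an all-data table on that definition. But 10.5.3.1 does not call the period double-blind. The final SAP added that description.

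Other points also carry weight:

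- A by-arm safety analysis free of open-label data is already planned in the SAP for the primary PFS analysis, and protocol 10.7.2 makes everything after Amendment 4 descriptive. This limits the consequence. It does not make the label correct.
- Adverse events are counted once per patient and category at maximum grade (3.7.1.3). Patients still on treatment already had some 43 to 55 months of follow-up. Protocol 1.2.1.2.1, on single-agent phase I data, describes neutropenia typically by Day 15 and QT changes in the first cycle. For such effects, late data change a table only through a new term, a higher grade, or a first relatedness or action entry.
- Laboratory grades use observed values only (3.7.2), and the notable criteria for vital signs and ECG intervals are numeric. Knowledge of treatment may affect unscheduled testing, but the argument about reporting and judgement does not carry over directly. ECG reading did move from central to local at Amendment 4 (protocol 7.2.2.6.1), which deserves a footnote.
- The final SAP names no field for an unblinding date, so availability of a patient-level date cannot be assumed.

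**Conclusion.** The point holds as a labelling fault with an asymmetric cut-off. The final SAP presents open-label data as double-blind in its by-arm safety tables and truncates only placebo patients who cross over. This follows from the text and needs no assumption.

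The open-label part is predominantly from the ribociclib arm: roughly 80-100% of contributing patients. That range rests on the PFS planning assumptions, on PFS as a proxy for time on treatment, and on unreported cross-over uptake. The models also differ widely in absolute numbers, for example 63 against 38 ribociclib patients.

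Two stronger readings are tempting. A reader might infer that almost all the open-label data come from the ribociclib arm. The documents do not establish this, because cross-over is optional, uptake is not given, and decliners stay in the period on fulvestrant alone. A reader might also infer that ribociclib event rates are inflated in one arm only. Placebo patients contribute open-label time too, and no post-unblinding event count or changed table entry can be derived from the documents. The inflation is possible in direction but not measured. Nor does the fault require cutting every safety table at unblinding. The SAP for the primary PFS analysis predates unblinding and is not affected.

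**What to change.** 1. In final SAP 2.1.8, rename the period, for example *randomized-treatment on-treatment period, including open-label time after unblinding*. Keep the protocol 10.5.3.1 definition for the all-data tables, and use the new label wherever section 3 refers to the period.
2. For adverse events, suspected relationship, events of special interest, and AE-related dose reduction, interruption and discontinuation (3.5.4, 3.5.5, 3.7.1.3-3.7.1.5), add by-arm tables that stop the day before unblinding. Use the patient's unblinding date or, if none is recorded, the site's Amendment 4 implementation date.
3. Report events after unblinding separately, by randomized arm.
4. For laboratory, vital-sign and ECG tables, correct the label and add a footnote. The ECG footnote should say that reading moved from central to local at Amendment 4.

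The cost is SAP wording, one derived date and some extra tables. The small downside is that late ribociclib events do not appear in the blinded-period comparison, but they remain in the all-data and post-unblinding tables.

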2.1.9 Last contact date

For patients not known to have died at the analysis cut-off, the last contact date will be derived using the last complete date among the following:

Table 2-1 Last contact date data sources

Source data	Conditions
Date of Randomization	No Condition
Last date patient was known to be alive from Survival Follow-up page	Patient status is reported to be alive, lost to follow-up or unknown.

Source data	Conditions
Start/End dates from further antineoplastic therapy	Non-missing medication/procedure term.
Start/End dates from drug administration record	Non-missing dose. Doses of 0 are allowed.
Date of discontinuation/study phase completion from end of treatment disposition page	No condition.
Date of discontinuation/Study phase completion from end of post treatment follow up phase disposition page	No condition
Date of ECG assessment	At least 1 non-missing parameter value
Date of PRO assessment	At least 1 non-missing answer to questionnaire
Tumor (RECIST) assessment date	For non-target lesion: non-missing lesion status For target lesion: non-missing lesion diameter For new lesion: "Is there a new lesion?" yes
Laboratory sample collection date	At least 1 non-missing parameter value
PK collection dates	At least 1 non-missing PK concentration
Vital signs date	At least one non-missing parameter value
Concomitant medication date	At least one non-missing name of medication
████████████████████	████████████████████
Body fluid/Tissue Collection date	Non-missing result (positive/negative tumor cells)
Hospitalization admission/discharge date	Non-missing type of facility admitted to
Cardiac imaging date	Non-missing LVEF or overall interpretation
Performance Status date	Non-missing performance status
Start/End dates of AE	Non-missing verbatim term

The last contact date is defined as the latest complete date from the above list on or before the data cut-off date. The cut-off date will not be used for last contact date, unless the patient was seen or contacted on that date. No dates post cut-off date will be used. Completely imputed dates (e.g., the analysis cut-off date programmatically imputed to replace the missing end date of a dose administration record) will not be used to derive the last contact date. Partial date imputation is allowed for event (death)/censoring coming from 'Survival information' eCRF.

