### **7.1.8 Lost to follow-up**

For patients whose status is unclear because they fail to appear for study visits without stating an intention to withdraw consent, the investigator should show "due diligence" by contacting the patient, family or family physician as agreed in the informed consent and by documenting in the source documents steps taken to contact the patient, e.g. dates of telephone calls, registered letters, etc. A patient should not be considered lost to follow-up until due diligence has been completed. Patients lost to follow up should be recorded as such on the appropriate Disposition CRF.

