### 10.5.1 Overall Survival

One of the secondary objectives of the study is to determine whether treatment with fulvestrant + ribociclib prolongs overall survival (OS) compared to treatment with fulvestrant + placebo.

OS is defined as the time from date of randomization to date of death due to any cause. If a patient is not known to have died, then OS will be censored at the date of last known date patient alive.

Assuming proportional hazards model for OS, the following statistical hypothesis for OS will be tested using a stratified log-rank test (stratified according to randomization stratification factors) at the one-sided 2.5% level of significance:

$H_0: \theta_2 \geq 0$  vs.  $H_a: \theta_2 < 0$

where  $\theta_2$  is the log-hazard ratio (fulvestrant+ribociclib arm vs. fulvestrant+placebo arm) of OS.

The analyses for OS will be based on the FAS. The distribution of OS will be compared between the two treatment groups using a stratified log-rank test at one-sided 2.5% level of significance.

[figure not shown]
The final OS analysis will not be performed at the time point of the final PFS analysis, but after additional follow-up. Therefore, a four-look design is considered for OS.

1. OS will be hierarchically tested (provided the primary PFS analysis is statistically significant) in the following way. The first potential time point for OS analysis will be at the time of the primary PFS analysis at which time approximately 161 deaths are expected. If PFS is statistically significant at this stage, OS will also be tested. If OS is not statistically significant at this stage, the 2nd OS analysis is planned after approximately 263 deaths are expected. If OS is not statistically significant at this stage, the final OS analysis will be planned after approximately 351 deaths.

The type I error probability for OS tests will be controlled by using a separate Lan-DeMets (O'Brien-Fleming) alpha spending function independent of the one used for the primary efficacy analysis of PFS at the one-sided type I error of  $\alpha=0.025$ . This guarantees the protection of the overall level  $\alpha = 2.5\%$  across the two hypotheses and the repeated testing of the OS hypotheses in the interim and the final analyses ([Glimm 2010](#)).

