2.1.9 Last contact date

For patients not known to have died at the analysis cut-off, the last contact date will be derived using the last complete date among the following:

Table 2-1 Last contact date data sources

Source data	Conditions
Date of Randomization	No Condition
Last date patient was known to be alive from Survival Follow-up page	Patient status is reported to be alive, lost to follow-up or unknown.
Start/End dates from further antineoplastic	Non-missing medication/procedure term.

Source data therapy	Conditions
Start/End dates from drug administration record	Non-missing dose. Doses of 0 are allowed.
Date of discontinuation/study phase completion from end of treatment disposition page	No condition.
Date of discontinuation/Study phase completion from end of post treatment follow up phase disposition page	No condition
Date of ECG assessment	At least 1 non-missing parameter value
Date of PRO assessment	At least 1 non-missing answer to questionnaire
Tumor (RECIST) assessment date	For non-target lesion: non-missing lesion status For target lesion: non-missing lesion diameter For new lesion: "Is there a new lesion?" yes
Laboratory sample collection date	At least 1 non-missing parameter value
PK collection dates	At least 1 non-missing PK concentration
Vital signs date	At least one non-missing parameter value
Concomitant medication date	At least one non-missing name of medication
████████████████████	████████████████████
Body fluid/Tissue Collection date	Non-missing result (positive/negative tumor cells)
Hospitalization admission/discharge date	Non-missing type of facility admitted to
Cardiac imaging date	Non-missing LVEF or overall interpretation
Performance Status date	Non-missing performance status
Start/End dates of AE	Non-missing verbatim term

The last contact date is defined as the latest complete date from the above list on or before the data cut-off date. The cut-off date will not be used for last contact date, unless the patient was seen or contacted on that date. No dates post cut-off date will be used. Completely imputed dates (e.g. the analysis cut-off date programmatically imputed to replace the missing end date of a dose administration record) will not be used to derive the last contact date. Partial date imputation is allowed for event (death)/censoring coming from 'Survival information' eCRF.

The last contact date will be used for censoring of patients in the analysis of overall survival.

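### For a patient lost to follow-up, the last-contact rule can let an unconditional disposition-page date override the last date known alive, so overall survival can be censored too late

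*SAP*

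**What the plan says.** **SAP for the primary PFS analysis, section 2.1.9.** The combination rule is a maximum: "The last contact date is defined as the latest complete date from the above list on or before the data cut-off date". Its purpose is also stated: "The last contact date will be used for censoring of patients in the analysis of overall survival". Section 3.8.2.1 repeats that OS is censored at last contact.

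Most rows of Table 2-1 require recorded data or a reported status. The randomisation date has no condition and needs none. Two other rows have none either: "Date of discontinuation/study phase completion from end of treatment disposition page" and "Date of discontinuation/Study phase completion from end of post treatment follow up phase disposition page". The survival-page row is "Last date patient was known to be alive from Survival Follow-up page", and it also applies when the status is lost or unknown. For the data cut-off the SAP sets a stricter test: "The cut-off date will not be used for last contact date, unless the patient was seen or contacted on that date".

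**Protocol.** For a patient not known to have died, section 10.5.1 says "then OS will be censored at the date of last known date patient alive". Appendix 2 (section 14.2.26, end dates) defines last contact as the last date known alive and uses the survival-page date when there is one. It falls back on the discontinuation date, defined there as the end of treatment visit, only when no survival follow-up is available. Loss to follow-up is a listed reason for stopping treatment (7.1.3) and for ending post-treatment follow-up (7.1.9). Section 7.1.8 adds: "A patient should not be considered lost to follow-up until due diligence has been completed".

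**SAP for the final CSR, section 2.1.9.** The same table and maximum rule appear, without the sentence on OS censoring. That SAP plans no OS analysis.

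**The concern.** A last contact date used for censoring should be a day on which the patient was known to be alive. A page completed because the patient could not be found need not carry such a date. If the site records the day it gave up, that day falls after the last real contact. Because the rule takes a maximum, it then displaces the survival-page date even where that page is correct.

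Such a patient stays in the OS risk set over a period in which a death would not have been seen. That can only raise the Kaplan-Meier curve of the arm concerned. OS is the secondary endpoint tested under type I error control, so its censoring date should follow the protocol's definition.

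The same date feeds the table of OS censoring reasons (section 3.8.2.1 of the primary SAP), where a patient counts as lost only if last contact is more than 98 days before cut-off. A late closure date can move a lost patient into the Alive category. It also enters the OS follow-up summaries in section 4.4.

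**Working it through.** **1. The rules side by side**

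| | Protocol (10.5.1, Appendix 2) | Primary-PFS SAP 2.1.9 |
|---|---|---|
| Target date | last date known alive | latest date in Table 2-1 |
| Survival-page date | takes precedence | one candidate among many |
| Discontinuation date | fallback only; a visit date | always a candidate, no condition |
| Post-treatment disposition date | not a listed source | always a candidate, no condition |

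The discrepancy is the missing condition and the missing precedence. Use of a discontinuation date as such is not the problem, since the protocol allows it as a fallback.

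**2. The plan's own OS figures.** Inputs from section 3.17 and Table 3-9 of the primary SAP: HR 0.71, one-sided 2.5%, 85% power, 2:1 allocation, looks at 161, 263 and 351 deaths. For a fixed design:

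d = (1.960 + 1.036)² / [(2/3)(1/3)(ln 0.71)²] = 8.978 / (0.2222 × 0.1173) ≈ 345 deaths.

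With three looks and the SAP's spending function (section 4.3.1), the bounds are 3.110, 2.353 and 2.013. Cumulative power is 14.4%, 60.7% and 85.0%, against 14%, 60% and 85% in the plan. These depend only on the number of deaths, which a later censoring date does not alter.

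**3. Size of late censoring.** The documents give neither the number lost nor the time from last contact to closure, so both are assumed. The simulation used:

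- 660 patients, 2:1, uniform accrual over 19 months, cut-off at month 56
- control medians of 38 months (40% of patients) and 26 months (60%), HR 0.71
- dropout independent of death, at a constant hazard −ln(1 − p)/46.5 per month, where 46.5 = 56 − 19/2
- 400 runs per scenario, each lost patient censored at true last contact and again at last contact plus the lag, capped at cut-off

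The 10% dropout is the plan's figure. The 15% and 5% split and the lags are assumptions. Every lost patient is treated as affected.

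| Lag (months) | Extra follow-up time, 10% in each arm | HR, 10% in each arm | HR, 15% ribociclib, 5% placebo | HR, 5% ribociclib, 15% placebo |
|---|---|---|---|---|
| 1 | 0.23% | 0.7109 → 0.7110 | 0.7241 → 0.7224 | 0.7180 → 0.7197 |
| 3 | 0.66% | 0.7221 → 0.7222 | 0.7168 → 0.7117 | 0.7109 → 0.7159 |
| 6 | 1.30% | 0.7147 → 0.7146 | 0.7151 → 0.7057 | 0.7127 → 0.7228 |
| 12 | 2.52% | 0.7131 → 0.7137 | 0.7157 → 0.6978 | 0.7166 → 0.7363 |

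About 45 patients were lost per run in the 10% scenario. Levels differ between cells because each scenario is a fresh set of runs, so only the paired change within a cell matters. With balanced loss the change is below 0.001. With unbalanced loss it is 0.002, 0.005, 0.009 and 0.018 downwards, or 0.002, 0.005, 0.010 and 0.020 upwards.

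**4. Survival within an arm.** Under a constant hazard the median is proportional to follow-up time divided by deaths. A 1.30% rise in follow-up time then lengthens a 30-month median by 30 × 0.0130 ≈ 0.4 months and a 42-month median by 42 × 0.0130 ≈ 0.5 months. This is approximate, because it applies the pooled percentage to each arm.

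**5. The censoring-reason table.** The threshold is 12 + 2 = 14 weeks, or 98 days. Suppose last contact was 6 months before cut-off (6 × 30.4375 ≈ 183 days) and closure came 3 months later, so 3 × 30.4375 ≈ 91 days before cut-off. By last contact the patient is lost (183 > 98). By the closure date the patient is Alive (91 < 98).

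**6. The final-CSR SAP.** The only use of last contact date found there is to cap the end of fulvestrant exposure for patients lost within 13 or 27 days of the last injection (section 3.5.1). Any error is therefore at most 27 days.

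**The case against.** The strongest reply is that no passage says which date a site enters for a lost patient. Section 7.1.8 governs when loss may be declared, not what date goes on the page. Section 7.1.3 ties the end-of-treatment page to stopping treatment, and Appendix 2 treats the discontinuation date as a visit. If sites enter the last visit or contact, the rule does no harm. This stands, and it makes the point conditional. The post-treatment row is the more exposed of the two.

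Second, the post-treatment page is completed before survival follow-up begins (7.1.9), and survival status is then sought every 12 weeks (7.1.7). Any later contact supersedes the disposition date, so only patients never reached again are affected. That also stands.

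Four stronger readings are tempting, and the documents do not support them:

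- **The reported OS benefit is biased.** The HR moves only if loss differs between arms, and the direction depends on which arm loses more. The documents give no loss by arm.
- **OS is in fact censored too late.** This needs the closure date to be what sites record, which is not stated.
- **The final-CSR SAP mis-censors OS.** It analyses no OS; its section 1.2 says the results are in earlier reports.
- **Loss to follow-up is concealed.** Only the OS censoring-reason table and the OS follow-up summaries could be affected. Both SAPs also tabulate reasons directly from the disposition pages (section 3.5 of the primary SAP, section 3.4 of the final one).

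**Conclusion.** The point holds as a specification gap in the primary-PFS SAP. Its OS censoring rule departs from the protocol's last-known-alive definition, from the precedence in Appendix 2, and from the test the SAP itself applies to the cut-off date. A lost patient can be censored too late if the page carries the closure date.

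The consequence is small. Each arm's survival estimate would be slightly too high. The treatment comparison is essentially unaffected under balanced loss, and under the assumed 15% against 5% imbalance the HR shift stays within about 0.02 either way for lags up to 12 months. These figures rest on assumed loss rates and lags, on dropout independent of death, and on every lost patient being affected. Nothing here suggests that the OS conclusion would change.

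In the final-CSR SAP the consequence is limited to the fulvestrant exposure cap, unless the rule is reused for a descriptive OS update, which protocol 10.5.1 leaves open.

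**What to change.** In Table 2-1, replace the absent condition on the two disposition rows with one: use the date only when the reason recorded on the page is not loss to follow-up. For lost patients, use the last-known-alive date from the survival page or, failing that, the latest dated clinical record, in line with Appendix 2. The reason is already collected on the page, so no new data are needed.

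Because OS has been tested and reported, apply this as a sensitivity re-run of OS censoring and of the censoring-reason table, not as a retrospective change to the primary analysis. Use the same rule in any later descriptive OS analysis and in the exposure cap of the final-CSR SAP. A first listing of lost patients whose disposition date is later than every other Table 2-1 date would show whether anyone is affected. If none is, the point is closed.

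Leave the dosing-record row, which accepts zero doses, as it is. A zero dose can be recorded at a real visit, and requiring a non-zero dose could discard true contacts.

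The cost is two table conditions, one program change and one re-run. Some lost patients may be censored earlier.
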